6.3 PATIENTS SETS ANALYSED

The following analysis sets will be defined for this trial:

Proprietary confidential information © 2018 Boehringer Ingelheim International GmbH or one or more of its affiliated companies

- Enrolled Set (ENR)

This patient set includes all patients with informed consent given. The enrolled set will be used for patient disposition tables.

- Treated Set (TS)

This patient set includes all patients who are documented to have received and taken at least one dose of any study medication during the treatment cycles (from day 1).

In the Phase Ib part, the TS includes the run-in period and will be used for all planned safety and efficacy analyses, unless otherwise specified (some analyses will be performed on the MTD set, details are provided in technical TSAP). In the Phase II part, the TS will be used for all planned safety analyses.

- MTD Set (MS)

The MTD set defines the set of patients in the Phase Ib part of the trial that are fully evaluable for determination of the MTD in the first treatment course. The MTD set will be used for some safety analyses in the Phase Ib part, this is specified in the technical TSAP. Patients in the Phase Ib part that are treated at the MTD after the MTD determination are not included in the MTD set (the list of patients included in the MTD Set is provided in a separate document that is archived in BIRDS).

Patients in the TS who were replaced within the MTD evaluation period in the Phase Ib part of the trial will be excluded from the determination of the MTD. Replacement of patients in the Phase Ib part of the study is defined in Section 3.3.5 of the CTP. The final list of replaced patients is supplied by the Trial Clinical Monitor (TCM) no later than the last report planning meeting before the database lock for the safety analysis.

- Randomised Set (RS)

This patient set includes all randomised patients in the Phase II part of the trial, regardless of whether or not they have received treatment. Patients are assigned to xentuzumab in combination with exemestane and everolimus or exemestane and everolimus alone as randomised. The randomised set will be used for the efficacy analyses of patients in the second part of the study.

Proprietary confidential information © 2018 Boehringer Ingelheim International GmbH or one or more of its affiliated companies

- ECG Set (ECGS)

This patient set includes all patients in the treated set who do not have an artificial cardiac pacemaker and have at least one on-treatment value (based on data collected until the safety cut-off date of 9th December 2016 (end of xentuzumab administration on 28th October 2016 + 42 days (length of REP)) for at least one ECG variable.

- ECG-PK Set

This patient set includes all patients in the ECG set from the Phase II part who are

[figure not shown]
- in the comparator group ('everolimus+exemestane') or
- in the 'xentuzumab + everolimus+exemestane' group and have at least one time-matching pair of valid xentuzumab plasma concentration and QTcF change from baseline (see [Section 7.8.4](#)).

The decision whether a concentration is considered valid will be made no later than at the final BRPM before DBL.

Please refer to [Section 7.8.4](#) for the definition of the maximum acceptable time deviation between PK blood sampling and ECG recording at different time points during the trial.

The analyses of ECG data will be based on the ECG set except those concerning the relationship between plasma concentrations and ECG variables which will be based on the ECG-PK set. Listings for patients with artificial pacemakers will be based on the TS.

No per protocol population will be used for analyses.

6.5 POOLING OF CENTRES

This section is not applicable because there are no inferential statistics, and therefore there is no statistical model in which centre/country can be included.

6.6 HANDLING OF MISSING DATA AND OUTLIERS

In general, missing data will not be imputed, unless required for the following analyses and definitions. Then the rules as described below apply.

Missing dates that affect the evaluation of endpoints specified in previous sections of this TSAP will be imputed utilising a “worst case” approach, which will be applied on a case-by-case basis (depending on the affected endpoint) and agreed to by the trial team members at the final BRPM before database lock at the latest.

Proprietary confidential information © 2018 Boehringer Ingelheim International GmbH or one or more of its affiliated companies

The rules in the Table 6.6: 1 below have been agreed by the trial and project teams, and will be used in this trial, if applicable.

Table 6.6: 1 Rules for imputations of missing or incomplete dates

Date	Imputation rule
Date of birth	In case only the year is given: 31 st of December
Date of death	Date last known to be alive. If only year and month are given: this will be imputed with 1 st of the month for the analysis of OS
Date of first histological diagnosis	1 st of month if day is missing 1 st of January if month also missing
Date of first appearance or recurrence of metastasis	1 st of month if day is missing 1 st of January if month also missing
Date of start of concomitant medication	No imputation required
Date of end of concomitant medication	No imputation required
Date of start of subsequent anti-cancer therapy (imputation required only for censoring of PFS)	If the day (respectively day and month) of the start date of subsequent anti-cancer therapy is missing, then the first of the month (respectively 1st January) will be imputed unless this date leads to a date before the stop date of study medications. In this case, the study medications stop date + 1 day will be imputed. Additionally, all imputed start dates of subsequent anti-cancer therapy should be before death date if available.
Date of stop of subsequent anti-cancer therapy	No imputation required
Date of end of treatment (only for patients still ongoing at time of snapshot/DBL)	Date of snapshot/DBL

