- d EOTV: If the decision to permanently discontinue all study treatments is taken during a scheduled visit, the End Of Treatment Visit (EOTV) should be performed instead of the scheduled visit (within 7 calendar days after last drug administration)
- f FU1 and Additional FU: All patients should have a follow-up 1 (FU1) visit 42 days (+7days) after the permanent discontinuation of study drugs. Patients who have not progressed and not started further treatment at FU1 should have additional limited follow-up visits at scheduled tumor assessment until progression, start of further anti-cancer treatment, consent withdrawal, lost to follow-up or death. See [Section 6.2.3](#)
- g OP: observation period every  $90 \pm 15$  days after the last follow-up visit (visit or phone contact allowed)
- h On Visits 2 and 4 of Courses 3 through 6, and on Visits 2, 3, 4 from Course 7 onwards, the study visit for patients on arm 1 (everolimus + exemestane) can be conducted via phone for collection of adverse events and concomitant medication

1. Written informed consent must be obtained before any protocol specific screening assessment is performed. Additional informed consent must be obtained prior to fresh tumor biopsy
2. Randomization: the randomization may take place up to 3 days prior to the C1V1 if site procedures require advance randomization to accommodate the logistics of dispensing study medication to patients. Sites that use this option must include a copy of site policy or documented justification in the ISF and submit a copy to the sponsor. If randomization is performed prior to C1V1, the subsequent visits must be scheduled with reference to C1V1. Arm 1 treatment: everolimus + exemestane; Arm 2 treatment: BI 836845 + everolimus + exemestane. Patient's screening, randomization and EOTV will be collected in the IRT system
3. Physical exam: includes a thorough cardiopulmonary, abdominal and lymph node exam and an assessment of the mental and neurological status. No need to repeat the physical exam on C1V1D1 if within three calendar days of the screening physical exam and the patient is deemed stable by the investigator
4. Vital signs: includes respiratory rate, pulse, temperature and blood pressure

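### SAP Table 6.6: 1 sets a death with unknown day to the 1st of the month for OS without a last-known-alive floor, so the imputed death can precede a date on which the patient was alive

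*SAP*

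**What the plan says.** The rule is one cell of Table 6.6: 1 in SAP section 6.6. It begins "Date last known to be alive. If only year and month are given", then gives the 1st as the imputed day, and closes with "of the month for the analysis of OS". The natural reading has two branches. A completely missing death date takes the date last known alive. A death date with month and year but no day takes the 1st of that month, for OS.

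The row for the start of subsequent anti-cancer therapy, in the same table, also uses the 1st of the month, but with two ordering checks. The lower check is that the date "will be imputed unless this date leads to a date before the stop date of study medications", in which case the day after the stop date is used. The upper check is that "all imputed start dates of subsequent anti-cancer therapy should be before death date if available".

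The text before the table says that missing dates affecting endpoints "will be imputed utilising a “worst case” approach, which will be applied on a case-by-case basis", to be settled by the final blinded report planning meeting at the latest. It then says that the table's rules "below have been agreed by the trial and project teams, and will be used in this trial, if applicable".

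Protocol section 7.4 says only that missing data are generally not imputed. It has no rule for a partial death date.

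**The concern.** The second branch states no lower bound. A patient who attended a visit, had a scan or answered a phone call late in the month of her death is recorded as dying on the 1st, before that contact. The row is also inverted in its use of information: a patient whose month of death is known can receive an earlier date than one with no death date at all, because only the latter is tied to the date last known alive.

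What is at stake is the validity of individual OS times. OS receives a stratified Cox model, Kaplan-Meier curves and a stratified log-rank test (Protocol section 7.3.2.1), and uses all available data (SAP section 7). Impossible orderings of contact and death would enter those outputs, and a zero or negative survival time could do so as well.

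**Working it through.** The plan states no figure for this rule, so there is nothing to reproduce. The check is date arithmetic, followed by an estimate of how often the fault would occur.

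**Inputs**
- The rule: SAP Table 6.6: 1, as above.
- Time in days: end date − randomisation date + 1. This is the SAP's form for PFS (section 5.1.2) and is assumed here for OS.
- Months = days × 12 / 365.25 (SAP section 7).
- Contact after follow-up: every 90 ± 15 "days after the last follow-up visit (visit or phone contact allowed") in the Phase II flow chart.
- Contact during treatment in Arm 2: weekly infusions (Protocol section 4.1.1.1).
- Calendar dates in the examples are assumed.

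**Example 1: contact in the month of death.** Randomised 11 January 2016, seen alive 29 August 2016, death recorded as August 2016.
- Rule as written: death on 1 August, OS = 203 + 1 = 204 days, or 204 × 12 / 365.25 = 6.70 months.
- With a last-known-alive floor: death on 29 August, OS = 231 + 1 = 232 days, or 7.62 months.
- The rule places death 232 − 204 = 28 days before she was seen alive.

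**Largest gap.** Contact on the 31st of a 31-day month: 31 − 1 = 30 days, or 30 × 12 / 365.25 = 0.99 month.

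**Example 2: randomised in the month of death.** Randomised 10 August, death recorded as August. The rule gives 1 August, so OS = −9 + 1 = −8 days.

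**How often, per death with a missing day.** Assume that death is uniform over a month of L = 365.25 / 12 = 30.44 days, contacts are g days apart, and death falls at a random point between contacts. The ordering is impossible when the last contact is on day 2 or later of that month.
- For g longer than a month, P = (L − 1)² / (2 × L × g), with (L − 1)² / 2 = 433.3.
  - g = 75: 433.3 / 2282.8 = 19%
  - g = 90: 433.3 / 2739.4 = 16%
  - g = 105: 433.3 / 3195.9 = 14%
- For g = 7, P = (L − 1 − 3.5) / L = 25.94 / 30.44 = 85%.

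A simulation under the same assumptions gives the same probabilities (0.190, 0.158, 0.136 and 0.852), and also gives the size of the shift:

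| Contact interval | Mean gap when the order is impossible | Mean days early, rule as written | Mean days early, with floor | Recovered by floor |
|---|---|---|---|---|
| 90 days | 10.3 | 14.7 | 13.1 | 1.6 |
| 7 days | 13.6 | 14.7 | 3.2 | 11.5 |

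The last column is what the missing floor costs per death with a missing day. The remaining days come from choosing the 1st of the month at all.

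**The case against.** **The sentence may mean something else.** The word 'this' in the cell could refer to a partial last-known-alive date instead of a partial death date. That reading is possible, but it leaves a partial death date with no rule in the table and still states no floor. The cell needs rewording either way.

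**A check may exist elsewhere.** The SAP's definition and analysis of OS are not in the available text, so a check there cannot be excluded. This stands as a limit. The imputation row itself is complete as printed and contains none.

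**The review meeting would catch it.** It might. But the review is described as a worst-case approach, which for OS points to an early date, and no floor is stated for it. An early date can be defended as conservative; a death before a recorded contact cannot.

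**Stronger readings that the documents do not support**
- A reader might take the average shift of about 15 days as the size of the fault. That figure belongs to the 1st-of-month convention for every partial date. With 90-day contacts the floor recovers only about 2 of those days.
- A reader might infer that the therapy-date check inherits the wrong death date. The 1st-of-month rule is limited to OS, and the therapy date is imputed only for PFS censoring. Nothing says that the OS-imputed death date is used there.
- A reader might expect 90-day telephone follow-up to be the worst setting. Per partial date it is where an impossible order is less likely (about 16%, against 85% with weekly contact), and the documents do not say where partial dates will arise.

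**Conclusion.** The point holds as a fault in a stated rule. On its natural reading, Table 6.6: 1 can date a death up to 30 days before the patient was known to be alive, and can give an OS below 1 day for a patient randomised in the month of death. The rates of about 14–19% with contacts 75–105 days apart and 85% with weekly contacts are per death with a missing day, and rest on uniform death dates and regular contacts.

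The consequence is minor. The number of such deaths is not given. Only those with a contact in the month of death are affected, and each shift is under one month. OS is listed among the other analyses with a nominal p-value, and no formal testing is planned (Protocol sections 7.1 and 7.3.2.1). The effect on the OS hazard ratio is therefore probably small, though it cannot be computed from the documents.

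**What to change.** Reword the date-of-death row of Table 6.6: 1 as two explicit branches. Date completely missing: the date last known alive, as now. Day missing: for OS, the later of the 1st of the recorded month and the date last known alive, and in no case before randomisation.

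Do not add a day to the last-known-alive date. A patient seen on 31 August with death recorded as August would then be given 1 September, outside the recorded month. Using the date itself also matches the branch for a completely missing date.

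The cost is one line in the table and one maximum in the derivation program. No new data are needed, since the date last known alive is already required by the first branch.

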Assessment will be performed at the following time points until progression/start of further treatment (tumor assessments after randomisation should be performed no more than 7 days prior to the scheduled tumor assessment date up to week 48 AND no more than 14 days prior to the scheduled tumor assessment date after week 48):

- At screening (within 28 days prior start of treatment):
- Every 8 weeks: during week 8 (49-56 days after randomisation), during week 16 (105-112 days after randomisation), during week 24 (161-168 days after randomisation), during week 32 (217-224 days after randomisation), during week 40 (273-280 days after randomisation), during week 48 (329-336 days after randomisation)
- Every 12 weeks after week 48 (e.g. during week 59-60 (406 – 420 days after randomisation), during week 71-72 (490 – 504 days after randomisation), etc.)

In the event of an interruption/delay to treatment, the tumor assessment schedule should not be changed. Patients who discontinue the trial for any reason other than imaging based progressive disease should have a tumour assessment (RECIST 1.1) performed at EOTV. Except in case of discontinuation from treatment due to imaging based progression, tumor assessment at EOTV is not necessary if the previous evaluation was done within 4 weeks of EOTV

Unscheduled scan based on the investigator's judgement is allowed and should also be documented in eCRF

16. Everolimus, if supplied by the sponsor, should be dispensed through IRT. The prescription of everolimus (if not supplied by the sponsor) and exemestane should be filled by pharmacy. Patient's screening, randomization, all drug dispensation visits and EOTV will be collected in the IRT system

17. Compliance check: on Day 1 of course 2, 3, 4, 5, etc. and at EOTV

18. For Course 2 only

19. Completion of the phase II part: Completion of the phase II part of the study should be recorded at FU (the last FU visit) when PD/death occurs, starting of new treatment, consent withdrawal or death

20. Collection of information on disease status and further therapies: information on progression, further anti-cancer treatment and death should be collected from patient's notes or by telephone contact with the patient. A formal study visit is not required

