## 5.1.2 Assessment of efficacy

### 5.1.2.1 Tumor response

Response and progression will be evaluated in this study using Response Evaluation Criteria in Solid Tumors (RECIST) guideline (version 1.1) ([R09-0262](#)). Tumor response will be assessed by local investigator's review.

For the Phase II part of the study, image acquisition will be performed as described in the Imaging Guideline (which will be filed in the ISF). Images will be collected and stored at a central facility assigned by the sponsor. The sponsor retains the option to perform an independent blinded central review of the study images at a later time.

See [APPENDIX 10.4](#), RECIST 1.1 (R09-0262) for details on lesion measurements and response assessment.

Every effort should be made to objectively evaluate tumor response for all patients who enter into the trial, including those who discontinue prematurely.

RECIST 1.1 will be followed in this study for tumor assessment. Tumor assessments should include scans of the chest, abdomen and pelvis. If clinically indicated, imaging of any other known or suspected sites of disease (e.g. breast, neck, brain etc) should be performed using an appropriate method (CT/MRI, etc.). Assessment will be performed at screening and then every 8 weeks after the first dose of BI 836845 (Phase I) or after randomization (Phase II) until week 48 and every 12 weeks thereafter. After screening, for each scheduled tumor assessment -7 days and -14 days windows are allowed, respectively before and after week 48. Tumor assessment does not need to be repeated at the screening visit if there are valid results available from assessments which were performed as part of routine clinical practice within 28 days prior to start of treatment. For the phase II part, these need to also meet the requirements in the Imaging Guideline. Patients who discontinue the trial for any reason other than imaging based progressive disease should have a tumour assessment (RECIST 1.1) performed at EOTV before starting new anti cancer therapies (exception to this are patients who have already had tumor assessment within 28 days of EOT visit)

In case of skin lesions, these should be measured with calliper and photographic documentation should be performed. However, skin lesion should not be considered as target lesion in this study.

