### **6.2.3 End of trial and follow-up period**

#### **6.2.3.1 End of treatment visit**

End of Treatment Visit (0-7 days after permanent discontinuation of study drugs)

Refer to the [Flow Chart](#) for details. The patient must return all study drugs, and the site must document the reason for permanent discontinuation of study medication. If permanent discontinuation of study drug occurs during a scheduled visit, examinations as defined for EOTV should be performed instead of the examinations for the scheduled visit.

Blood samples for soluble biomarkers (for all patients), PK and immunogenicity (for patients on BI 836845 regimen) must be obtained.

In patients who are experiencing disease progression at EOTV of the phase II part, a fresh tumor biopsy should be performed from those with appropriate informed consent.

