Death but no progression, zero or one missed radiological assessment prior to death	Event	Date of death
Death without progression, but two or more consecutively missed radiological assessments prior to death	Censored	Date of last radiological assessment prior to missed assessments
Initiation of subsequent anti-cancer therapy		
Subsequent anti-cancer therapy started before progression or death	Censored	Date of last radiological assessment before subsequent anti-cancer therapy
No baseline and/or post-baseline imaging and subsequent-anti cancer therapy started prior to a death	Censored	Date of randomisation (or first treatment administration, in non-randomised trials)

In order to identify that consecutive imaging timepoints are missing for a given patient, a nominal time point [8, 16, 24, 32, 40, 48 weeks, and every 12 weeks thereafter] will be assigned to each and every image. This is achieved by creating windows for every RECIST assessment. The windows are defined in [Table 6.7.2: 1](#).

Last evaluable imaging

An evaluable radiological image for the censoring of PFS is an image for which an overall response assessment of SD, Non-CR/Non-PD, PR or CR has been assigned. This is used for censoring of patients without progression at end of trial, or censoring prior to missed assessments, or censoring prior to subsequent anti-cancer therapy.

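### The imputed start of subsequent anti-cancer therapy is not bounded by a documented progression, so in patients who stopped study drug before the progression scan a PFS event can become a censored time

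*SAP*

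**What the plan says.** The row for subsequent therapy in SAP Table 6.6: 1 (Section 6.6) serves one purpose: "imputation required only for censoring of PFS". When the day is missing it uses the 1st of the month, and when the month is missing too it uses 1 January. That date "will be imputed unless this date leads to a date before the stop date of study medications". For the exception the row says: "In this case, the study medications stop date + 1 day will be imputed". It adds that "all imputed start dates of subsequent anti-cancer therapy should be before death date if available". It does not mention the date of a documented progression.

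SAP Table 5.1.2: 1 (Section 5.1.2) uses the resulting date. In the situation "Subsequent anti-cancer therapy started before progression or death", PFS is censored at the last radiological assessment before the therapy. Without that entry, a patient who progressed with at most one missed scan is an event on the date of the progression scan.

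The protocol provides for scans after study drug has stopped:
- The end-of-treatment visit falls 0 to 7 days after discontinuation (Section 6.2.3.1). Patients who stop without imaging progression should have a scan "performed at EOTV before starting new anti cancer therapies", unless one was done within 28 days (Section 5.1.2.1).
- Patients who stop early, including those with clinical progression only, continue with scans every 8 or 12 weeks (Section 5.1.2.1).
- Footnote 15 of the Phase II flow chart gives the end point of the schedule: "Assessment will be performed at the following time points until progression/start of further treatment".

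**The concern.** Progression is a usual reason for starting the next line of treatment, so progression and the new therapy will often share a calendar month. In a patient already off study drug, the 1st of that month, or the day after the last dose, can lie before the scan that prompted the new therapy. The analysis then puts therapy before progression when the true order was the reverse, and drops the event.

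Such a patient has progressed but is carried as progression-free up to an earlier scan. Because the end-of-treatment scan is waived when another was done within 28 days, the censoring date in that setting will normally be more than four weeks before the progression. The censoring depends on the outcome. It affects patients who stop before progression, and in an open-label trial where one arm adds weekly infusions the frequency of that could differ between arms.

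**Working it through.** **Inputs.** S is the date all study medication stopped, P the progression scan and T the true start of the next therapy. The imputation rule is from SAP Table 6.6: 1, the PFS rules from SAP Table 5.1.2: 1, and the scan timing from Protocol Sections 5.1.2.1 and 6.2.3.1. Planned events and probabilities are from Protocol Section 7.6. I assume that a therapy date equal to P does not count as before progression.

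**The plan's own figure.** Protocol Table 7.6: 2 gives 69% for an observed hazard ratio of 0.8 or less with 90 events and a true value of 0.72. With standard error 2/√90 = 0.211, Φ((ln 0.8 − ln 0.72)/0.211) = Φ(0.500) = 0.691. It reproduces.

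**The rule.** Let c be the 1st of the recorded month (1 January if only the year is known). The imputed date is c if c is on or after S, and otherwise S + 1. The event is lost if the imputed date is before P.

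**When it fails.**
- S on or after P: the imputed date is never before S, so never before P. The event is kept.
- S at least 2 days before P, day missing, T in the same month as P: if c is on or after S, the imputed date is the 1st, and the event is lost unless P is itself the 1st. If c is before S, the imputed date is S + 1, at most P − 1, and the event is lost. Both branches fail.
- S one day before P: the event is kept, except when S is the 1st and P the 2nd with T in that month. The 1st is then not before the stop date and is used.
- Day missing, T in a later month than P: c is after P and the event is kept.
- Month missing: the same logic with 1 January, so almost any P in the same year as T is exposed.

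**Worked cases** (2016 dates):

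| Case | S | P | T | Imputed, day missing | PFS | Imputed, month also missing | PFS |
|---|---|---|---|---|---|---|---|
| A | 5 Mar | 11 Mar (end-of-treatment scan) | 25 Mar | 6 Mar | censored | 6 Mar | censored |
| B | 10 Feb | 8 Mar (off-drug scan) | 22 Mar | 1 Mar | censored | 11 Feb | censored |
| C | 11 Mar | 11 Mar | 25 Mar | 12 Mar | event | 12 Mar | event |
| D | 5 Mar | 11 Mar | 4 Apr | 1 Apr | event | 6 Mar | censored |

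**Share of exposed patients lost.** Take patients with S at least 2 days before P and an assumed gap of g days from P to T. With the day missing, a month of L days loses P on days 2 to L − g, which is L − 1 − g days. Summed over 2016 this is 366 − 12(g + 1). It is divided by the 365 progression dates run, 1 January to 30 December.

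| g (days) | Lost, day missing |
|---|---|
| 3 | 318/365 = 87% |
| 7 | 270/365 = 74% |
| 14 | 186/365 = 51% |
| 21 | 102/365 = 28% |
| 28 | 18/365 = 5% |

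With the month also missing, the share runs from 99% (g = 3) to 92% (g = 28). These shares apply only to exposed patients with a partial date. The documents give neither the gap nor the number of such patients.

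**Precision.** If 3, 5 or 9 of 90 events were lost (assumed numbers, with the hazard ratio itself undistorted), the 69.1% becomes 68.8%, 68.6% or 68.2%. For 81 events: Φ(0.1054/(2/√81)) = Φ(0.474) = 0.682.

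**The case against.** The strongest reply is that this is an edge case. Treatment beyond progression is not allowed (Protocol Section 3.1) and documented progression requires withdrawal from therapy (Section 3.3.4.1). When progression is found on treatment, the stop date is therefore normally on or after the scan and the fallback date is harmless. A loss needs all study drug stopped before the scan, a partial therapy date and, if only the day is missing, progression and therapy in the same month. The primary analysis also uses response assessments only up to 25 November 2016, after recruitment stopped on 28 October 2016, and the trial is exploratory with no formal testing. All of this stands. It limits how many patients are affected but does not make the rule right for those who are.

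A second reply is that SAP Section 6.6 provides for case-by-case, worst-case handling of missing dates, agreed by the final blinded report planning meeting. That gives a route for correcting an obvious conflict, but no commitment to do so. Worst case is not defined for this date, and the same section says the table rules have been agreed and will be used. Nor do the two PFS sensitivity analyses in SAP Section 7.4.2.2 help: one uses all response data and the other the IRT stratification, and neither varies this rule.

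**Conclusion.** The concern holds within a limited scope. Followed as written, the rule gives a wrong PFS status to some patients who stopped all study medication at least 2 days before a scan showing progression and whose next-therapy date is partial. Their number is unknown and may be zero. The issue is informative misclassification of the primary endpoint, not loss of precision. This assumes that the stop date means the end of all study medications.

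Four stronger readings are tempting but not supported:
- A reader might infer that nearly all such progressions are lost, since 29 of 30 days (97%) fall after the 1st of a 30-day month. That already assumes progression and therapy share a month; without that condition the day-missing share is 87% down to 5%, depending on the gap.
- A reader might put a count on the patients affected. The documents give no rate of partial dates or of stopping before progression.
- A reader might say that the rule contradicts the protocol or reverses the worst-case principle. The protocol's scan-before-therapy instruction is worded as a recommendation with an exception, and it covers the end-of-treatment scan, not every off-drug scan. An early date is also a recognisable conservative choice for a start date.
- A reader might infer a bias towards one arm. The direction is unknown.

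**What to change.** Add to the row in SAP Table 6.6: 1: *If only the day is missing and radiological progression is documented in the recorded month, impute the later of the current rule and the date of progression + 1 day, without leaving the recorded month and respecting the death bound. If progression is on the last day of the month, use that day and keep the progression as an event.* Case A then becomes 12 March and case B 9 March, both events at the progression scan. Case C and the day-missing version of case D are unchanged.

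If the month is also missing, keep the current rule, list these patients, and repeat the PFS analysis with documented progression counted as an event. Bounding year-only dates by progression in the primary analysis would go too far. A patient who stopped in January, began therapy in February (recorded as the year only) and had progression recorded in October would become an October event.

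List every patient whose PFS status depends on an imputed therapy date. If there are none, the listing settles the matter.

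The cost is one sentence, a small programming change, one listing and one repeat analysis. The downside is that a patient who truly started the next therapy earlier in the same month as progression would count as an event at the progression scan.
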